5.5.6 Infusion-related reactions

Infusion-related reactions to cisplatin or carboplatin and etoposide should follow the guidelines below. If etoposide cannot be used again, etoposide phosphate may be substitute.

Table 4 Infusion Reaction Treatment Guidelines for MK-3475

NCI CTCAE Grade	Treatment	Premedication at subsequent dosing

Grade 1 Mild reaction; infusion interruption not indicated; intervention not indicated
	
Increase monitoring of vital signs as medically indicated until the subject is deemed medically stable in the opinion of the investigator.
	
None

Grade 2 Requires infusion interruption but responds promptly to symptomatic treatment (e.g., antihistamines, NSAIDS, narcotics, IV fluids); prophylactic medications indicated for < =24 hrs
	
Stop Infusion and monitor symptoms. Additional appropriate medical therapy may include but is not limited to: IV fluids Antihistamines NSAIDS Acetaminophen Narcotics
 
Increase monitoring of vital signs as medically indicated until the subject is deemed medically stable in the opinion of the investigator. If symptoms resolve within one hour of stopping drug infusion, the infusion may be restarted at 50% of the original infusion rate (e.g., from 100 mL/hr to 50 mL/hr). Otherwise dosing will be held until symptoms resolve and the subject should be premedicated for the next scheduled dose. Subjects who develop Grade 2 toxicity despite adequate premedication should be permanently discontinued from further trial treatment administration.
	
Subject may be premedicated 1.5h (± 30 minutes) prior to infusion of pembrolizumab (MK-3475) with: Diphenhydramine 50 mg po (or equivalent dose of antihistamine). Acetaminophen 500-1000 mg po (or equivalent dose of antipyretic).


Grades 3 or 4 Grade 3: Prolonged (i.e., not rapidly responsive to symptomatic medication and/or brief interruption of infusion); recurrence of symptoms following initial improvement; hospitalization indicated for other clinical sequelae (e.g., renal impairment, pulmonary infiltrates) Grade 4: Life-threatening; pressor or ventilatory support indicated
	
Stop Infusion. Additional appropriate medical therapy may include but is not limited to: IV fluids Antihistamines NSAIDS Acetaminophen Narcotics Oxygen Pressors Corticosteroids Epinephrine
 
Increase monitoring of vital signs as medically indicated until the subject is deemed medically stable in the opinion of the investigator. Hospitalization may be indicated. Subject is permanently discontinued from further trial treatment administration.
	
No subsequent dosing

Appropriate resuscitation equipment should be available in the room and a physician readily available during the period of drug administration.
		

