5.2 Trial Treatment

The treatment to be used in this trial is outlined below:

Table 2 Trial Treatment

Cohort	Drug	Dose/Potency	Dose Frequency	Route of Administration	Regimen/Treatment Period	Use
A and B ¹	Pembrolizumab	200 mg	Q3W	IV infusion	Day 1 of each 3 week cycle	Experimental
	carboplatin OR	AUC 6	Q3W	IV infusion	Day 1 of each 3 week cycle	Standard care
	cisplatin	75 mg/m ²	Q3W	IV infusion	Day 1 of each 3 week cycle	Standard of care
	Etoposide	100 mg/m ²	Q3W	IV infusion	Days 1, 2, 3 of each 3 week cycle	Standard of care
C	Pembrolizumab	200 mg	Q3W	IV infusion	Day 1 of each 3 week cycle	Experimental
D	Pembrolizumab	200 mg	Q3W	IV infusion	Day 1 of each 3 week cycle	Experimental

¹for cohort A, the number of total cycles of chemotherapy will be 4-6 total, while pembrolizumab will continue as long as disease has not progressed or patient not removed from study for other reasons for up to 2 years. For cohort B, patients should have received 1 cycle platinum + etoposide prior to entry onto study, so the total number of cycles during study will be 3-5 (such that the TOTAL number of cycles on or off study is a MINIMUM of 4 and a MAXIMUM of 6).

Trial treatment should begin on the day of randomization or as close as possible to the date on which treatment is allocated/assigned.

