5.5.5 Timing of Administration

Pembrolizumab will be administered at least 30 minutes prior to premedication for the chemotherapies.

Trial treatment should be administered on Day 1 (or days 1, 2, and 3 for etoposide) of each cycle after all procedures/assessments have been completed.

All trial treatments will be administered on an out-patient basis.

For subjects who experience disease progression, investigators may elect to interrupt treatment by deferring the decision to continue/discontinue treatment in the trial until confirmation of disease progression per RECIST 1.1 at least 28 days from the date of imaging demonstrating disease progression. Subjects for whom disease progression is not confirmed on subsequent imaging may resume treatment.

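### Section 5.5.6 sends platinum and etoposide infusion reactions to a table written for pembrolizumab, whose stop rule, read literally, ends chemotherapy and pembrolizumab together

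*Combined protocol and SAP*

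**What the plan says.** Section 5.5.6 opens: "Infusion-related reactions to cisplatin or carboplatin and etoposide should follow the guidelines below". What follows is headed "Table 4 Infusion Reaction Treatment Guidelines for MK-3475", and the section contains no other guideline. The opening paragraph does not mention reactions to pembrolizumab itself. It does add: "If etoposide cannot be used again, etoposide phosphate may be substitute".

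Within Table 4:

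- The grade 2 premedication entry is timed 1.5 hours (plus or minus 30 minutes) "prior to infusion of pembrolizumab (MK-3475) with" an antihistamine and an antipyretic.
- The grade 2 treatment entry ends: "Subjects who develop Grade 2 toxicity despite adequate premedication should be permanently discontinued from further trial treatment administration".
- The grade 3 or 4 entry ends: "Subject is permanently discontinued from further trial treatment administration".

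Two places show what trial treatment covers. Section 5.2 introduces Table 2 with "The treatment to be used in this trial is outlined below", and for cohorts A and B that table lists pembrolizumab, carboplatin or cisplatin, and etoposide. Section 5.5.5 says "Trial treatment should be administered on Day 1 (or days 1, 2, and 3 for etoposide) of each cycle".

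Elsewhere, Sections 5.3 and 5.3.2 leave dose changes and delays of platinum and etoposide to institutional standards. Table 3 in Section 5.3.2 governs pembrolizumab. Its infusion reaction row calls for permanent discontinuation at grades 3-4, and the note beneath it requires a permanent stop after any life-threatening event.

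**The concern.** The stop rule is an operative instruction, and it is attached to the wrong drugs. A participant in cohort A or B who reacts to etoposide could, on the literal text, lose platinum, etoposide and pembrolizumab for good. For a patient with extensive-stage small cell lung cancer that means losing first-line chemotherapy and the investigational drug over a reaction that pembrolizumab did not cause. Another site, relying on the etoposide phosphate sentence, could change the etoposide formulation and carry on with everything else. The protocol provides for several sites (Sections 4.4.3 and 4.5.2), so the same event could be handled in opposite ways. Exposure in the two combination cohorts would then vary for reasons unrelated to the drug's effect, and this would carry into the secondary progression-free survival, overall survival and safety results.

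**Working it through.** The plan states no figure on this point, so the check is mainly a comparison of text.

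1. **Which rule applies.** The Section 5.5.6 lead-in names platinum and etoposide and points to what lies below. Only Table 4 lies below.

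2. **Which drug the table fits.** Its title and its premedication timing refer to pembrolizumab. Chemotherapy infusions per cycle are platinum on day 1 plus etoposide on days 1, 2 and 3: 1 + 3 = 4. Pembrolizumab is given on day 1 only, so 2 of the 4 (etoposide on days 2 and 3) have no same-day pembrolizumab infusion to which premedication could be timed. This shows that the table was not written for chemotherapy; it does not measure harm.

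3. **What the stop covers.** Table 2 and Section 5.5.5 both use trial treatment for the whole regimen in cohorts A and B. The literal stop is therefore a stop of all drugs.

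4. **A chemotherapy reaction, grade by grade:**

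| Reaction to chemotherapy | Table 4, read literally | Table 3, for pembrolizumab |
|---|---|---|
| Grade 2, first occurrence | Further dosing allowed | No infusion reaction entry at this grade |
| Grade 2 despite premedication | All trial treatment ends | No infusion reaction entry at this grade |
| Grade 3 | All trial treatment ends | Permanent stop; the context points to reactions to pembrolizumab |
| Grade 4 | All trial treatment ends | Stop after any life-threatening event, so the same result for pembrolizumab |

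5. **Against the etoposide phosphate sentence.** If Table 4 bars etoposide, it also bars every other trial drug, so there is no remaining regimen in which to use the substitute. The sentence keeps a role only where Table 4 does not stop treatment, for example after a first grade 2 reaction that leads the clinician to abandon etoposide.

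6. **Against Sections 5.3 and 5.3.2.** These send chemotherapy modifications and delays to institutional standards but do not name infusion reactions. The tension is real but indirect.

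7. **How many participants.** Exposed: 15 + 15 = 30 of 60. The documents give no incidence, so the following is assumption only. If a proportion p of participants has a chemotherapy reaction at a grade that triggers Table 4's stop, the expected number is 30p and the chance of at least one is 1 - (1 - p)^30.
   - p = 1%: 0.3 participants; 1 - 0.99^30 = 26.0%
   - p = 3%: 0.9 participants; 1 - 0.97^30 = 59.9%
   - p = 5%: 1.5 participants; 1 - 0.95^30 = 78.5%

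   These are chances that a qualifying reaction occurs. Harm also requires that the site apply the table literally.

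**The case against.** Several counter-arguments have weight. The etoposide phosphate sentence stands next to the referral to Table 4 and could be read as an exception to it. A specific infusion reaction rule can coexist with a general institutional-standards rule. Premedication in Table 4 is optional, and Section 5.5.5 mentions chemotherapy premedication separately. On day 1 the drugs are given close together, so a cautious stop after a severe reaction is defensible. Progression-free and overall survival run from registration, so stopping treatment removes nobody from the analysis. Institutional standards may also differ between sites.

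These points limit the size of the problem, but they do not remove it. Nothing marks the etoposide phosphate sentence as an exception, and it says nothing about pembrolizumab or platinum. Caution over uncertain attribution on day 1 does not explain a rule that also ends pembrolizumab after an etoposide reaction on day 2 or 3.

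Three stronger readings are tempting, and the documents do not support them.

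- A reader might infer that Table 3 leaves grade 3 unclear for pembrolizumab, because its infusion reaction row names no causal drug. The row does state permanent discontinuation. The paragraph introducing Table 3 opens with events associated with pembrolizumab, the closing row covers all other drug-related toxicity, and the cross-referenced Section 5.8.3 applies to events judged related to pembrolizumab. One looser phrase about severe or life-threatening events does not outweigh that context.
- A reader might infer that Tables 3 and 4 conflict at grade 2. Table 3 has no grade 2 infusion reaction entry, and silence in one table beside a specific rule in the other is not a conflict. Table 3's footnote on persistent grade 2 events belongs to a different row.
- A reader might infer that Section 5.3.2 already lets pembrolizumab continue alone after a chemotherapy reaction. That sentence covers only delays of more than 4 weeks for hematologic or other laboratory toxicity.

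**Conclusion.** The point holds as an error in an operative rule, most likely a drafting slip. Section 5.5.6 applies a pembrolizumab table to chemotherapy reactions. Taken at its word, it ends the whole regimen for grade 2 despite premedication and for grade 3 or 4. This is hard to reconcile with the etoposide phosphate sentence beside it and is in indirect tension with Sections 5.3 and 5.3.2. At grade 4 the consequence for pembrolizumab matches Table 3, so the problem there concerns chemotherapy only.

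The reach is limited to cohorts A and B, 30 of 60 planned participants. The number affected is probably small: 0.3 to 1.5 participants under assumed risks of 1% to 5%, which do not come from the documents. Cohorts C and D receive no chemotherapy on study, and the primary PD-L1 endpoint is not touched. The case for correction rests on what an affected participant could lose, on consistent handling across sites, and on how little the change costs.

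**What to change.** Reword Section 5.5.6 as follows.

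- State that Table 4 governs infusion reactions to pembrolizumab, and that permanent discontinuation in Table 4 means discontinuation of pembrolizumab.
- State that reactions to cisplatin, carboplatin or etoposide are managed by institutional standards, including substitution of etoposide phosphate, and that only the agent judged responsible is stopped.
- State that Table 3 continues to govern pembrolizumab, including its stop after any life-threatening event.

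Table 3 needs no amendment. An express permission to continue pembrolizumab after a grade 3 reaction, on attribution alone, is a debatable clinical choice and is not needed to remove the error.

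The cost is a few sentences in a protocol amendment. A physician already judges the relationship of each adverse event to pembrolizumab (Table 6, Section 10.4), so no new data collection is required, and the sample size and analyses are unchanged. Some variation between sites in managing chemotherapy reactions will remain, as it already does for other chemotherapy modifications under Sections 5.3 and 5.3.2.

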5.5.7 Other treatments

For participants on cohorts A and B who may be candidates for consolidation thoracic radiation or PCI after the completion of initial platinum-based therapy, pembrolizumab dosing should be halted 2 weeks prior to initiation of radiation and restarted no earlier than 2 weeks post-completion of radiation. For participants on this study, the total dose of thoracic radiation should not exceed 3000 cGy given in 10 fractions.

5.6 Administration

Infuse pembrolizumab (MK-3475) over approximately 30 minutes, with a window of -5 and + 10 minutes, through a peripheral line or indwelling catheter. A sterile, non-pyrogenic, low-protein binding 0.2 to 5 µm in-line filter made of polyethersulfone (PES) must be used during administration to remove any adventitious particles. If the infusion set does not contain 0.2 to 5 µm in-line filter, it is recommended to use 0.2 to 5 µm add-on filter which may contain an extension line (Note: the materials of the extension line and filter should be as mentioned above). Please refer to the pharmacy manual for further details.

5.7 Subject Compliance Monitoring

Subjects who are significantly non-compliant with protocol required visits, assessments, and dosing instructions may be withdrawn from the study by the investigator and/or sponsor. The investigator and/or sponsor have the right to discontinue a subject from study treatment or withdraw a patient from the study at any time.

5.7.1 Criteria for Taking a Participant Off Study

Participants will be removed from study when any of the following criteria apply:

- Lost to follow-up
- Withdrawal of consent for data submission
- Death

The reason for taking a participant off study, and the date the participant was removed, must be documented in the case report form (CRF).

5.7.2 Participant replacement strategy

Participants in this study will not be replaced unless if there is not sufficient tissue to evaluate the primary endpoint (PD-L1 expression) from either archival or pre-treatment biopsies from at least 12 participants. Tissue evaluation will be ongoing in real time to determine adequacy of assessment. Initial tissue adequacy assessment from diagnostic biopsy specimens will be required prior to starting on therapy to minimize this risk.

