FOR COHORTS A AND B ONLY: Initial enrollment will include only 3 participants, who may be enrolled into either cohort A or B. Once these three participants have cleared cycle 1, an additional 3 participants may be enrolled into either cohort A or B if no DLTs are seen. If < 2 DLTs are seen in the first 6 participants, enrollment to the rest of the cohorts will proceed. If ≥ 2 DLTs are seen, enrollment will be halted and discussion of dosing change with Merck and the overall PI will occur prior to further enrollment. Based on safety data to date with other platinum-based regimens, we do not anticipate interactions that would necessitate dosing change, so there will not be pre-specified dose reductions planned. Cohorts A and B will be pooled for the purposes of DLT evaluation as the treatment regimen after study initiation is identical.

Cohort C: participants will have previously received 4-6 cycles of platinum-based therapy and have stable disease. In addition, these patients must not be candidates for further consolidation thoracic radiotherapy or PCI. Pembrolizumab treatment should start no sooner than 2 weeks and no later than 6 weeks from the start of the last cycle of chemotherapy. Therapy will continue for up to 34 cycles (2 years).

Cohort D: participants will have previously received 4-6 cycles of platinum-based chemotherapy and thoracic radiation therapy or PCI or both. Pembrolizumab treatment should start no sooner than 2 weeks and no later than 6 weeks from the start of the last dose of radiation. Therapy will continue for up to 34 cycles (2 years).

Treatment will be administered on an outpatient basis. Reported adverse events and potential risks are described in Section 1.8.1. Appropriate dose modifications are described in Section 5. No investigational or commercial agents or therapies other than those described below may be administered with the intent to treat the participant's malignancy.

All patients will be required to have a tissue biopsy within 3 weeks of study entry and after completion of prior therapy (see section 6.6.7.1). For cohort A, this time frame could be up to 6 weeks.

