5.3.1 Definition of Dose-Limiting Toxicity (DLT)

Dose-limiting toxicities are defined as any hematologic or non-hematologic toxicity of grade 3 or above possibly attributable to drug that does not resolve within 12 weeks with or without steroids (and steroids

must be able to be tapered to <10 mg po qd within that time frame). Although the DLT period is officially the 1st two cycles, if any participant experiences a grade 3, 4, or 5 toxicity, they will be closely monitored. If those participants are not able to resume treatment within 6 weeks (2 cycles), enrollment into cohorts A and B will be halted to allow for a full 12 week evaluation prior to further enrollment.

For cohorts A and B only: initially 3 participants will be enrolled. When those three participants have completed the DLT evaluation period (2 cycles), if 0 of 3 have experienced a DLT (defined as hematologic or non-hematologic toxicity of grade 3 or above possibly attributable to drug that does not resolve within 12 weeks with or without steroids), the study may continue to enroll an additional 3 participants for DLT monitoring. If 1 of 3 participants experiences a DLT, an additional 3 participants will be enrolled and followed. If ≥ 2 participants experiences a DLT (either when 3 or when 6 enrolled), further enrollment will be halted for discussion between Merck and the overall PI to determine whether additional enrollment should continue or if dose modifications should be made. If no more than 1 of 6 participants experiences a DLT, full enrollment of the cohort may proceed.

Management and dose modifications associated with the above adverse events are outlined below.

Number of Participants with DLT during initial 3 participant enrollment	Continuation Decision Rule
0 out of 3	Enroll 3 additional participants and monitor for DLT.
≥ 2	Further enrollment will be stopped until discussions re: dose modification between Merck and overall PI determine whether further dose levels should be explored.
1 out of 3	Enter at least 3 more participants and monitor for DLT. 
• If 0 of these 3 participants experience DLT, proceed with complete enrollment of the cohort.• If 1 or more of this group suffer DLT, then further enrollment will be stopped until discussions re: dose modification between Merck and overall PI determine whether further enrollment should continue and if dose modification is required.

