5.3.2 Dose Delays/Dose Modifications

Dose delays and modifications of cisplatin or carboplatin and etoposide should follow institutional standards (namely, that participants meet re-treatment criteria prior to re-initiation of therapy and may be dose-reduced per institutional standards). However, if dosing of chemotherapy that occurs concurrently with pembrolizumab is held (cohorts A and B), then that day's dosing of pembrolizumab should also be held. If dose –delay of chemotherapy for hematologic or other laboratory toxicity results in a > 4 week delay in therapy, chemotherapy should be discontinued and pembrolizumab may continue as monotherapy. Exceptions to this may be reviewed on a case-by-case basis with sponsor.

Adverse events (both non-serious and serious) associated with pembrolizumab exposure may represent an immunologic etiology. These adverse events may occur shortly after the first dose or several months after the last dose of treatment. Pembrolizumab must be withheld for drug-related

toxicities and severe or life-threatening AEs as per Table 3 below. See Section 5.8.3 for supportive care guidelines, including use of corticosteroids.

Table 3. Toxicity Management and Dose Reduction/Delay/Discontinuation

Toxicity	Hold Treatment For Grade	Timing for Restarting Treatment	Discontinue Subject
Diarrhea/Colitis	2-3	Toxicity resolves to Grade 0-1.	Toxicity does not resolve within 12 weeks of last dose or inability to reduce corticosteroid to 10 mg or less of prednisone or equivalent per day within 12 weeks.
	4	Permanently discontinue	Permanently discontinue
AST, ALT, or Increased Bilirubin	2	Toxicity resolves to Grade 0-1	Toxicity does not resolve within 12 weeks of last dose.
	3-4	Permanently discontinue (see exception below) ¹	Permanently discontinue
Type 1 diabetes mellitus (if new onset) or Hyperglycemia	T1DM or 3-4	Hold pembrolizumab for new onset Type 1 diabetes mellitus or Grade 3-4 hyperglycemia associated with evidence of beta cell failure.	Resume pembrolizumab when patients are clinically and metabolically stable.
Hypophysitis	2-3	Toxicity resolves to Grade 0-1	Toxicity does not resolve within 12 weeks of last dose or inability to reduce corticosteroid to 10 mg or less of prednisone or equivalent per day within 12 weeks.
	4	Permanently discontinue	Permanently discontinue

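### The cohort A/B safety run-in counts participants enrolled rather than observed, so it can clear the combination on fewer than six observed participants or stall at its first gate

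*Combined protocol and SAP*

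**What the plan says.** Cohorts A and B share one run-in of 3 and then 6 participants, described in the synopsis (Trial Procedures), Section 5.3 and Section 5.3.1.

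- **First gate.** Section 5.3: "Once these three participants have cleared cycle 1, an additional 3 participants may be enrolled into either cohort A or B", provided no DLT is seen. The synopsis also refers to cycle 1. Section 5.3.1 asks for more: "When those three participants have completed the DLT evaluation period (2 cycles), if 0 of 3 have experienced a DLT", the next three may enter. It adds: "Although the DLT period is officially the 1st two cycles".
- **After 1 DLT in 3.** The Section 5.3.1 table says: "Enter at least 3 more participants and monitor for DLT".
- **Final clearance.** Section 5.3: "If < 2 DLTs are seen in the first 6 participants, enrollment to the rest of the cohorts will proceed". Section 5.3.1: "If no more than 1 of 6 participants experiences a DLT, full enrollment of the cohort may proceed". Neither sentence requires the second three to have completed the window.
- **Existing halt.** Under Section 5.3.1, if a participant with a grade 3, 4 or 5 toxicity cannot resume treatment within 6 weeks, A/B enrolment stops for a full 12-week evaluation.
- **Replacement.** Section 5.7.2: "Participants in this study will not be replaced unless if there is not sufficient tissue to evaluate the primary endpoint (PD-L1 expression"; the rest of that sentence ties the exception to having at least 12 participants with usable tissue. Section 4.5.2 cancels the registration of anyone who never receives protocol therapy.

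No section defines a DLT-evaluable participant or says how to classify one who is dosed and then leaves the window without a DLT.

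**The concern.** A run-in of six is informative only if all six are watched through the window. Here the denominator is enrolment. A dosed participant may leave through early progression, death from disease, withdrawal or loss to follow-up, without a toxicity that triggers the halt. The text then leads to one of two outcomes:

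- **In the second three:** the participant stays among the 6 with no DLT recorded, so clearance can rest on five, four or even three observed participants.
- **In the first three:** the Section 5.3.1 condition that all three complete 2 cycles is never met, and no section provides a substitute. Under the cycle 1 wording of Section 5.3 and the synopsis, someone who leaves in cycle 2 passes after half the window.

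Sites could therefore read the same text differently. Each cohort is planned at 15, so up to 30 − 6 = 24 further participants would receive the combination after clearance. This gate is the only pre-specified numerical safety rule that precedes them. Some loss is foreseeable: Section 9.1 expects dropout from inability to continue therapy, and Section 4.1 admits extensive-stage disease with ECOG performance status up to 2.

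**Working it through.** The plan states no operating characteristics for the run-in, so there is no figure of its own to reproduce.

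**Inputs from the documents.** Clearance at no more than 1 DLT in 6, with the run-in continuing after 1 of 3 (Section 5.3.1).

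**Assumptions.** The documents give neither the true DLT rate p nor the per-participant chance d of leaving the window unobserved. I take p from 10% to 50% and d from 5% to 20%. The upper value of d equals the whole-study loss implied by 15 enrolled and 12 analysable (3/15, Section 9.1), so it is high for a window of two cycles. Loss is taken as independent of DLT.

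**Step 1: clearance with k participants observed and the rest counted as non-DLT.**

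P(clear) = (1−p)^k + k·p·(1−p)^(k−1)

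At p = 0.33:
- k = 6: 0.67^6 + 6(0.33)(0.67^5) = 0.0905 + 0.2673 = 0.358
- k = 5: 0.67^5 + 5(0.33)(0.67^4) = 0.1350 + 0.3325 = 0.468

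| True DLT rate | 6 observed | 5 | 4 | 3 |
|---|---|---|---|---|
| 10% | 88.6% | 91.9% | 94.8% | 97.2% |
| 20% | 65.5% | 73.7% | 81.9% | 89.6% |
| 33% | 35.8% | 46.8% | 59.9% | 74.5% |
| 40% | 23.3% | 33.7% | 47.5% | 64.8% |
| 50% | 10.9% | 18.8% | 31.3% | 50.0% |

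**Step 2: how often someone is lost.** P(at least one of n lost) = 1 − (1−d)^n.

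| Loss d | At least one of first 3 | At least one of 6 |
|---|---|---|
| 5% | 14.3% | 26.5% |
| 10% | 27.1% | 46.9% |
| 15% | 38.6% | 62.3% |
| 20% | 48.8% | 73.8% |

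Losing two or more of six, which the columns for four or fewer observed need, has probability 11.4% at d = 10% and 22.4% at d = 15%.

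**Step 3: clearance averaged over loss, at p = 0.33.** A participant who can be lost shows a DLT with probability q = p(1−d).

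- *Any of the six can be lost:* (1−q)^6 + 6q(1−q)^5. At d = 15%, q = 0.2805, giving 0.1387 + 0.3245 = 0.463.
- *Only the second three can be lost* (the first three complete, as Section 5.3.1 requires): (1−p)^3·[(1−q)^3 + 3q(1−q)^2] + 3p(1−p)^2·(1−q)^3. At d = 15%: 0.3008 × 0.8081 + 0.4444 × 0.3725 = 0.2431 + 0.1655 = 0.409.

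| Loss d | Only second three | Any of six |
|---|---|---|
| 0 | 35.8% | 35.8% |
| 5% | 37.4% | 39.1% |
| 10% | 39.1% | 42.7% |
| 15% | 40.9% | 46.3% |
| 20% | 42.6% | 50.1% |

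**Step 4: low-toxicity case.** At p = 10% and d = 15% in any of the six, q = 0.085 and clearance is 0.5868 + 0.3271 = 0.914, against 0.886 with no loss.

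**The case against.** Much of the case against this point stands, and it limits the size.

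- **Toxicity-driven exits are largely caught.** The Section 5.3.1 halt covers a participant with grade 3–5 toxicity who cannot resume within 6 weeks. What remains is mainly exits without such toxicity.
- **Stopping treatment does not end observation.** Adverse events are followed for 30 days (Section 5.11), and serious ones are reported to 90 days, or to 30 days if new anticancer therapy starts (Section 10.3). A last dose on day 22 gives cover to about day 52, past the 42-day window. The gap is mostly exits after one dose, death, withdrawal of consent and loss to follow-up.
- **The 1-of-3 branch has slack.** It allows at least three more, but only in that branch.

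Four stronger readings are tempting, and the documents do not support them:

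- *That the plan scores early leavers as DLT-free.* No sentence says so. It is inferred from the enrolled denominator.
- *That Section 5.7.2 was written to stop a DLT slot being refilled.* Its exception concerns the number analysable for PD-L1. Letting the next planned enrollee take the slot adds nobody and is arguably not replacement at all. The difficulty is that no section says this.
- *That held doses create unobserved participants.* For a day when concurrent chemotherapy is held, Section 5.3.2 says that "dosing of pembrolizumab should also be held", but the same section restarts the cycle and its assessments after a delay. The participant stays under observation.
- *That this gate is the only formal safety check.* The data safety monitoring committee reviews adverse events quarterly (Section 10.5.1), the principal investigator reviews them monthly (Section 12.1), and serious events are reported within 24 hours (Section 10.3). None of these carries a numerical DLT rule.

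**Conclusion.** The point holds in a limited form. As written, the run-in can clear the combination on fewer than six observed participants, or stall at three, and no rule settles which participants count. One unobserved participant raises the chance of clearing a combination with a 33% DLT rate from 36% to 47%. Averaged over 15% loss, the rise is to about 41% if the first three must complete and 46% if any of the six can be lost. At a 10% DLT rate the change is under 3 percentage points. All these figures rest on assumed DLT and loss rates and on the inference that a leaver counts as a non-DLT. Given the existing halt and the continuing safety follow-up, I would call this a cheap improvement rather than an essential correction.

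**What to change.** 1. In Section 5.3.1, define DLT-evaluable: received the combination and either had a DLT or was observed to the end of the DLT period. State that the two gates need 3 and 6 DLT-evaluable participants.
2. In Section 5.7.2, state that the next A/B enrollee fills an open DLT slot within the planned 30, and that the non-evaluable participant stays in all other analyses.
3. Reconcile the synopsis, Sections 5.3, 5.3.1 and 5.7.2 on the window (cycle 1 or 2 cycles) and on the denominator. The reconciled text should also say how DLT status is assigned when the window ends, since the definition turns on non-resolution within 12 weeks while the window lasts 6.

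The cost is protocol wording and possible delay: the gate may open some weeks later if someone leaves early. Allowing for loss, about 7 participants would be needed for six evaluable at 5–10% loss (6/0.95 = 6.3; 6/0.90 = 6.7) and 8 at 20% (6/0.80 = 7.5), all within the 30 planned. With six evaluable participants guaranteed, the chance of clearance is that of the 6-observed column above.
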